6.1.2 Measurement of Ataxia and Functioning

6.1.2.1 Spinocerebellar Ataxia Functional Index (SCAFI)

The SCAFI consists of a timed 8MWT to be carried out at maximum speed, the 9-hole peg test with both dominant and non-dominant hands (9HPT-D; 9HPT-ND) and the "PATA" test to measure speech performance. For the 8MWT and 9HPT tests, a lower score/time indicates a clinical improvement. A higher "PATA" test score indicates improvement in speech performance [Schmitz-Hübsch et al, 2008].

The SCAFI represents vital movement features (8MWT;9HPD-D/-ND for evaluation of the coordination of the upper extremities; PATA-test for evaluation of speech). After the assessment, raw scores are transformed into reciprocals and converted into subtest Z-scores. The final SCAFI is then generated as the arithmetic mean of all three Z-scores.

Two subtests, the 9HPT-D and 8MWT, will be videoed in a standardized format at every visit, except Visit 0.

A subset of the SCAFI, the 9HPT-D, serves as an inclusion criterion for the severity of ataxia at the beginning of the study prior to enrollment.

The complete SCAFI will be performed at the time points designated on the schedule of events (Appendix 3A for "naïve" patients and Appendix 3B for "non-naïve" patients).

The score will be assessed by the investigator or qualified member of the study team.

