5 PARENT STUDY: STATISTICAL ANALYSIS

5.1 General considerations

The Parent study is considered the study period between screening (Visit 0 or Visit 1) through Visit 6.

Raw data (in listings) will be presented in the same precision as received. Appropriate rounding will be performed for the following summary statistics, where applicable: mean, standard deviation (SD) and two-sided 90% confidence limits will be presented with at least one more decimal than the original data; minimum and maximum values will be presented with the same precision as the original data. In frequency tables, percentages will be presented with 1 decimal unless otherwise stated.

P-values will be presented with 3 decimals, and those smaller than 0.001 will be replaced by <0.001. One-sided p-values smaller than 0.05 will be considered statistically significant for the primary endpoint and indicative for other endpoints. No adjustment for multiple comparisons will be applied. Conclusions regarding treatment efficacy will not solely rely on detecting statistical significance but equal emphasis will be placed on the magnitude and clinical relevance of treatment differences as judged by the point estimates. All evaluations other than the primary endpoint will be considered exploratory in nature.

Descriptive statistics presented in general summary tables will be the number of non-missing observations (n), mean, SD, minimum, median and maximum for quantitative data. For categorical data, frequency counts and percentages will be determined.

In general, baseline is defined as the value measured prior to first study treatment administration (at Visit 2), unless otherwise specified. In case no value at Visit 2 is available, the value measured at Visit 1 will be used. A footnote may be added to those tables/listings presenting baseline value, with an explanation how this value was assessed.

If available in the database, data for screening failures will not be presented in summary tables, except for disposition, medical history and end-of-study displays. Data for screening failures will be listed as available.

A treatment emergent adverse event (TEAE) is defined as an adverse event that appears during or after study treatment and was absent before.

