5.6.3 Additional secondary endpoints

All additional secondary endpoints will be presented using the mITT and PPS populations, and all individual data will be listed as well. No sensitivity analysis will be applied.

Measurement of Ataxia and Functioning

- SARA total score
- SCAFI total score
 - o 9HPT-D

Clinical Study Reference: IB1001-202

- 9HPT-ND
- o 8MWT
- PATA test

Descriptive statistics will be used to summarize the endpoints above at each visit.

The subscores of the SARA score (gait, stance, sitting, speech disturbance, finger chase, nosefinger test, fast alternating hand movements, heel-shin slide) will also be summarized for each visit using descriptive statistics. Stacked bar charts will be provided per visit, based on the subscores of the total SARA score.

Spaghetti plots of individual patient SARA total scores and the SCAFI total scores versus time will be made as well as a mean or median display versus time, depending upon the distribution, and corresponding two-sided 90% CI at each visit.

The average SCAFI subscores (8MW_avg, 9HPT-D_avg, 9HPT-ND_avg and PATA_avg) as determined according to Section 10.1, following the scoring manual, will also be summarized with descriptive statistics.

The changes in SARA total score, SCAFI total score, the SCAFI subscores (8MW_avg, 9HPT-D_avg, and PATA_avg) between Visit 2 and Visit 4, as well as the changes between Visit 4 and Visit 6 will be analysed using a one-sample t-test or a Wilcoxon Signed Rank test depending on the distribution of the data. The SCAFI subscore 9HPT-ND_avg will only be descriptively summarized in tabular format.

Measurement of Health-related Quality of Life

The results of EQ-5D-5L as well as the EQ-5D-Y will be combined into a 5-digit number presenting the health status of the subject. Frequency tables will be presented per visit for the 5 domains, as well as for the 5-digit number of the EQ-5D-5L and the EQ-5D-Y separately. In addition, EQ-5D-5L and EQ-5D-Y domain percentages will be presented in separate bar charts per visit, with all visits combined into one plot (if possible).

The EQ-VAS score will be summarized by visit using descriptive statistics for patients aged < and \geq 18 years combined. Spaghetti plots of individual patient EQ-VAS scores versus time will be made as well as a mean or median display versus time, depending upon the distribution, and corresponding two-sided 90% CI at each visit.

Measurement of Overall Neurological Status

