After the adjustments made for 8MWT and 9HPT as above, SCAFI total score will be calculated as follows:

The mean of the trial1 and trial2 scores are determined for each subtest/hand, and referred to as: $8MW_avg$, $9HPT-D_avg$, $9HPT-ND_avg$ and $PATA_avg$. In case a subtest is only performed once, this value is taken as the mean. Then, the 8MW and 9HPT performance times are converted to the same dimension as the PATA rate, as follows: $8MW_recipr = 1/8MW_avg$, $9HPT_recipr = (1/9HPT-D_avg + 1/9HPT-ND_avg)/2$. Note that 8MW and 9HPT performance times cannot be 0.

Then each is converted into a Z-score using the following algorithms:

- 8MW_zscore = (8MW_recipr BL(mean 8MW_recipr)) / BL(SD 8MW_recipr)
- 9HPT_zscore = (9HPT_recipr BL(mean 9HPT_recipr)) / BL(SD 9HPT_recipr)
- PATA zscore = (PATA avg BL(mean PATA avg)) / BL(SD PATA avg)

where BL means baseline value and SD means standard deviation. The mean 8MW_recipr and SD 8MW_recipr are determined using the SAF analysis population.

In case of missing values, the following applies:

- The cases with either 8MW, 9HPT (in one or both hands) or PATA tests not performed at all ("unable to perform due to physical limitations" or "not performed for other reason") are excluded from the calculation of baseline means.
- Only when an 8MW score, 9HPT score or PATA score is missing due to "unable to perform due to physical limitations", then a substitution will be applied as follows:
 - $\circ~$ When 8MW tests were not performed, then 8MW_recipr will be substituted by 1/1800~s.
 - When 9HPT tests were not performed: if only data for one hand is missing, then 9HPT_avg=3000 s for that specific hand; when data for both hands are missing, then 9HPT_recipr=1/3000 s.

• When PATA tests were not performed, then PATA_avg is substituted with 0. For agreement on "unable to perform due to physical limitations" or "not performed for other reason", the sponsor will be contacted. The missings created for 8MWT and 9HPT as stated above are considered "unable to perform due to physical limitations".

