According to the "SCAFI rating manual", the SCAFI total score is to be determined as the arithmetic mean of the 3 Z-scores. However, following explanation of IntraBio and [name], the SCAFI score needs to be calculated as the mean of the non-missing Z-scores. The SCAFI score can only be determined if at least one test is actually performed, i.e. in case all tests were imputed because of missing values, no SCAFI score will be determined. This contradicts the "SCAFI rating manual".

SARA

Clinical Study Reference: IB1001-202

The overall SARA score is reported as provided in the eCRF. For presentation of the subscore results, the individual results as provided in the eCRF will be used, where for the subscores finger chase, nose-finger test, fast alternating hand movements, heel-shin slide this is the average value for the two sides (left and right) as determined per eCRF.

mDRS

The mDRS composite score is calculated as a sum of the separate subscores divided by 24. If one of the subscores is missing, the mDRS composite score is missing as well. As compared to the official questionnaire, the eCRF allows values of 0 ('normal') for the subscores.

Laboratory

Laboratory safety data measurements that are denoted as smaller/larger than a certain value (e.g. < x.x), will be imputed with this value (e.g. x.x) for calculations of descriptive statistics. Listings will show the value as collected, and a footnote will be added to the summary tables for explanation.

Comments

The following data are either not collected or only collected as free text fields in the eCRF/database or lack relevant information in the database, and it is therefore necessary that these details are added in the programming code manually. The decisions to drive this manual coding may be documented and finalized during the BDRM but can already be maintained/discussed during the course of the trial for efficiency.

- The reason for video unavailability is recorded as free text field, and it needs to be deducted if any of these reasons consider a "technical issue". The sponsor will provide input.
- PATA score missing due to "unable to perform due to physical limitations" is not available as such in the database but needs to be deducted from a free comment field. The sponsor will provide input.

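### A tested SCAFI change can compare different sets of subtests, because SAP 10.1 averages whichever Z-scores exist at each visit

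*SAP*

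**What the plan says.** Protocol 6.1.2.1 builds SCAFI from the 8-metre walk, the 9-hole peg test and the PATA speech test: "The final SCAFI is then generated as the arithmetic mean of all three Z-scores". It gives no rule for a missing subtest.

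SAP 10.1 treats missing subtests in two ways.

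- **Physical inability.** The substitution clause opens "Only when an 8MW score, 9HPT score or PATA score is missing due to" and goes on to name physical limitations. The floor values are 1/1800 s for the walk reciprocal, 3000 s for the peg test and 0 for PATA. Walks done with disallowed support, and peg tests left without a usable time because of the 300-second limit, are put in this class.
- **Any other reason.** Nothing is substituted. The SAP says "the SCAFI score needs to be calculated as the mean of the non-missing Z-scores", and adds: "The SCAFI score can only be determined if at least one test is actually performed".

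The SAP acknowledges that this contradicts the SCAFI rating manual and attributes it to an explanation from the sponsor. SAP Section 7, which collects changes to the protocol, does not list it.

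Under SAP 5.6.3, the SCAFI changes from Visit 2 to 4 and from Visit 4 to 6 "will be analysed using a one-sample t-test or a Wilcoxon Signed Rank test depending on the distribution of the data". The same section rules out sensitivity analyses for these endpoints. On interpretation, SAP 5.1 says: "One-sided p-values smaller than 0.05 will be considered statistically significant for the primary endpoint and indicative for other endpoints".

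**The concern.** A change score should compare the same thing at two times. Under this rule a patient can have a three-subtest mean at one visit and a two-subtest or one-subtest mean at the other. The difference then mixes real change with a change in what was averaged. Because patients may be much better at one subtest than another, the second part can be sizeable in an individual with no clinical change.

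At stake is the reading of two planned tests on the SCAFI total, in a study with about 36 patients in the primary analysis set, where a few mismatched scores carry weight. The SAP is stricter elsewhere: in the same section, the mDRS composite is set to missing if any subscore is missing.

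**Working it through.** The plan states no effect size, power or expected missingness for SCAFI, so there is no figure of its own to reproduce.

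**1. The artefact in one patient.** Let a, b and c be the three Z-scores, identical at both visits, with a missed for a non-physical reason at the later visit only.

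- Earlier visit: (a + b + c)/3
- Later visit: (b + c)/2
- False change: (b + c)/2 - (a + b + c)/3 = [(b + c)/2 - a]/3

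With a = -1, b = 0, c = +1: (0.5 + 1)/3 = +0.5. If the same test is back at Visit 6, the Visit 4-6 change shows -0.5. If the +1 test is the one missed, the Visit 2-4 sign reverses: (-0.5 - 1)/3 = -0.5.

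**2. Typical size.** Write the false change as -a/3 + (b + c)/6. For unit-variance Z-scores with common correlation r (assumed), its mean is 0 and its variance is 1/9 + 2/36 + 2r(-2/18 + 1/36) = (1 - r)/6.

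| r (assumed) | SD of false change |
|---|---|
| 0.3 | 0.34 |
| 0.5 | 0.29 |
| 0.7 | 0.22 |

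**3. Effect on the test.** Simulation of the one-sided 5% one-sample t-test with no true change. From the plan: n = 36 (the mITT target) and the one-sided 5% level. Assumed: change SD 0.3, r = 0.5, 3 patients affected.

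| Which subtest is missing in the 3 patients | One-sided error |
|---|---|
| None missing | 4.9% |
| One named subtest, at random | 5.0% |
| One named subtest, only among the weaker half on it | 7.4% |
| Each patient's own worst subtest, every time | 10.8% |
| All three patients given exactly +0.5 | 16.0% |

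The last row is a bound, not an expectation: +0.5 is 0.5/0.29 = 1.7 SDs of the random artefact, and all three must fall in the same direction. Even when the worst subtest is always the one lost, the mean artefact is about +0.30.

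A second simulation put noise of SD 0.3 on each component at each visit (n = 36, r = 0.5), with the walk missing at Visit 4. With 2, 4 or 6 patients affected, the error was 5.1%, 4.9% and 5.1% when they were chosen at random, and 6.7%, 8.7% and 11.0% when they came from the weaker half of walkers.

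**4. After the fix.** If only components present at both visits are used, the false change is (b + c)/2 - (b + c)/2 = 0. In the second simulation the error was then 4.9% to 5.2% in every setting with n = 36.

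**The case against.** The strongest reply is that the SAP already closes the most dangerous route. A subtest the patient is too impaired to do is not dropped but receives a severe floor value. Only gaps for other reasons drop out, and nothing in the documents suggests that these follow a patient's weakest subtest. A reader might infer that the rule systematically turns the loss of the worst test into improvement, or that the error is about 16%. The documents do not support either: random gaps leave the error near 5%, and 16% requires an identical favourable artefact in every affected patient.

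The gaps may also be rare. The full SCAFI is scheduled at Visits 2, 4 and 6. Under the COVID-19 provisions, Visits 4 and 6 may be postponed but not skipped and must be in person. A missing Visit 2 value is replaced by Visit 1 (SAP 5.1), and SAP Section 7 mentions repeat visits where measurements were incomplete. The walk, dominant-hand peg test and PATA changes are tested separately and individual scores are listed, so an artefact could be spotted. The rule is also deliberate and disclosed as a departure from the manual.

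Most of this stands and limits the size of the problem. It does not remove the mismatch. Protocol 10.4 allows visits at alternative locations and foresees that some assessments cannot be done there, so gaps at the tested visits remain possible. The sponsor also decides from free-text comments which gaps count as physical, so the component set depends partly on judgement in an open-label study.

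**Conclusion.** The point holds as a defect of definition with modest expected consequences. As written, SAP 10.1 lets a tested SCAFI change be non-zero when nothing has changed, and SAP Section 7 does not record the departure from protocol 6.1.2.1.

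The t-test is biased on average only if non-physical gaps are related to how well the patient does on the missing subtest. In that case the one-sided error is about 7-11% with 3 of 36 patients affected; otherwise the rule adds noise and the error stays near 5%. The number affected, the correlation and the change SD are all assumptions, because the documents give none of them. The primary endpoint does not use SCAFI, and SCAFI p-values are indicative only. The correction is worth making because it is cheap and removes the artefact exactly.

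**What to change.** In SAP 10.1, add one sentence: each tested SCAFI change (Visit 2-4 and Visit 4-6) is computed only from the component Z-scores available, whether observed or substituted, at both visits of that pair. Keep the mean of non-missing Z-scores for by-visit tables and plots. List the departure from protocol 6.1.2.1 in SAP Section 7.

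The cost is a few lines of code and no new data. There are two downsides. Some patients will contribute fewer components, and their two changes may rest on different components. A tested change may also not equal the difference between the tabulated by-visit scores, which a table footnote should say.

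Requiring all three Z-scores, observed or substituted, would be simpler and closer to the protocol, but it drops every patient with a non-physical gap at either visit of the pair.

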8.6 Missing Data

Analyses based on the mITTe analysis set will utilize a last observation carried forward (LOCF) approach for a missing score at Visit 9.

For the primary mDRS endpoint this implies that the score of Visit 8 will be used instead. Other endpoints will not be imputed, and missing data will be reported as is. No sensitivity analyses will be applied.

For all other endpoints there will be no imputation for missing data and data will be reported and evaluated as observed.

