4.2.1 Primary endpoint

The primary endpoint in the Extension phase is "success" based on the mDRS score, with success defined as no change or improvement (decrease) in the mDRS score from Visit 7 to Visit 9.

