6.6 Statistical analysis efficacy endpoints

The analysis for all efficacy endpoints in the Extension phase is the mITTe.

Analyses of the primary endpoint based on the mITTe population will utilise a last observation carried forward (LOCF) approach for missing mDRS at Visit 9. For the primary mDRS endpoint this implies that the measurement of Visit 8 will be used instead. Other endpoints will not be imputed, and missing data will be reported as is. No sensitivity analyses will be applied.

For the primary endpoint for the Extension phase there will be separate descriptive statistical displays within the key subgroups as listed in Section 6.5.3, without any statistical analysis. For the subgroup presentations, only the mITTe population will be used. No plots will be created. All individual primary endpoint data will be listed as well.

All efficacy endpoints for Extension phase Visit 10 to Visit 12 are considered exploratory, and therefore described under section 6.6.4.

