6.6.1 Primary endpoint Extension phase

The primary efficacy endpoint is based on the Modified Disability Rating Scale (mDRS). The mDRS measures neurological status via clinical signs and symptoms in 6 domains (ambulation, language, manipulation, swallowing, seizures, and ocular movement). A higher mDRS score indicates a clinical worsening, while a lower mDRS score indicates a clinical improvement. A 0-point change in the mDRS score represents a stabilization of disease progression, which is also considered a significant clinical improvement.

The mDRS composite score and individual domains, including change values, will be summarized using descriptive statistics at each visit for Extension phase.

The primary endpoint in this Extension Phase is success measured on the mDRS score from the Extension Phase baseline (Visit 7) to the end of treatment in the Extension Phase (Visit 9). Success is defined as no change or a decrease in mDRS score from Visit 7 to Visit 9.

The primary endpoint will be summarized using a frequency table. The primary statistical analysis of comparing the proportion success with the null proportion of 0.10 will be done using a one-sided Fisher's Exact Test, expecting an increase in the success rate. The statistical result (one-sided p-value and exact 90% confidence interval²) will be added to the frequency table. This analysis is considered to be exploratory.

In addition, a spaghetti plot presenting the total mDRS scores of each patient through time will be created.

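### Extension primary endpoint: a partly scored Visit 9 mDRS that already proves worsening can be replaced by Visit 8 and counted as a success

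*SAP*

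**What the plan says.** The Extension primary endpoint is binary. SAP 4.2.1 has "success defined as no change or improvement (decrease) in the mDRS score from Visit 7 to Visit 9", and SAP 6.6.1 repeats this. SAP 6.6.1 also lists the six domains and gives the direction: "A higher mDRS score indicates a clinical worsening, while a lower mDRS score indicates a clinical improvement".

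SAP 10.1 (mDRS) forms the composite as the sum of the domain scores divided by 24, then states: "If one of the subscores is missing, the mDRS composite score is missing as well". It also records that "the eCRF allows values of 0 ('normal') for the subscores".

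For a missing Visit 9 mDRS, SAP 6.6 carries the last observation forward: "For the primary mDRS endpoint this implies that the measurement of Visit 8 will be used instead". Protocol Appendix 6 Section 8.6 agrees: "For the primary mDRS endpoint this implies that the score of Visit 8 will be used instead". Both sections say that no sensitivity analysis will be done.

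SAP 3.2.1 admits to the mITTe any treated patient with an mDRS score at Visit 7 and at Visit 8, Visit 9 or both. Neither document separates a Visit 9 that did not happen from one that was attended but only partly scored.

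**The concern.** The endpoint asks one question: is the Visit 9 total above the Visit 7 total? Five of six domains can be enough to answer it. If those five already sum to more than all six did at Visit 7, no value of the blank domain can bring the patient back to success.

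The written rules do not use that information for the classification. They declare the composite missing and substitute the Day 180 score. A patient known to be worse at Day 365 can then be entered as stable, and SAP 6.6.1 regards stability as a clinically meaningful gain. At the planned size of 20, the test turns on very few patients.

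**Working it through.** **Inputs.** Composite = sum of six domains / 24, missing if any domain is missing (SAP 10.1). Lowest domain value 0, labelled normal (SAP 10.1); that nothing lies below normal is my reading of that label. Higher is worse (SAP 6.6.1). Visit 8 replaces a missing Visit 9 (SAP 6.6; Protocol Appendix 6 Section 8.6). n = 20, null rate 10%, alternative 31%, stated power 80% (SAP 2.4.2; Protocol Appendix 6 Section 8.10). One-sided 5% level (Protocol Appendix 6 Section 8.5.1).

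**1. The plan's own figure.** The comparison is one sample against a fixed 10%, so I used the exact binomial. The smallest r with P(X ≥ r | 20, 0.10) ≤ 0.05 is r = 5:
- P(X ≥ 4 | 0.10) = 0.133
- P(X ≥ 5 | 0.10) = 0.043 (exact level 0.0432)
- P(X ≥ 5 | 0.31) = 0.791

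The stated 80% is reproduced at 79.1% and is not in dispute.

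**2. The lower bound.** Let S9 be the sum of the observed Visit 9 domains and T7 the full Visit 7 total. No blank domain is below 0, so the Visit 9 total is at least S9. If S9 > T7, failure is certain. Dividing both by 24 changes nothing.

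**3. A constructed record.** The domain order is ambulation, manipulation, language, swallowing, seizures, ocular movement.

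| Visit | Domains | Sum | Composite under SAP 10.1 |
|---|---|---|---|
| 7 | 2, 1, 1, 1, 0, 1 | 6 | 6/24 = 0.250 |
| 8 | 2, 1, 1, 1, 0, 1 | 6 | 6/24 = 0.250 |
| 9 | 3, 1, 1, 2, blank, 1 | at least 8 | missing (at least 8/24 = 0.333) |

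Worsening is certain, since 8 > 6. Under the written rules Visit 9 is missing, Visit 8 is used, the change is 0.250 − 0.250 = 0, and the patient is a success.

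**4. When this happens.** Four conditions must meet in one patient:
- Visit 9 is attended but partly scored.
- The Visit 8 composite is complete.
- Visit 8 is not above Visit 7.
- S9 > T7.

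If Visit 8 is already above Visit 7, the patient fails under either rule. If Visit 8 is also incomplete, no composite exists after Visit 7 and the patient leaves the mITTe.

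**5. Size, as illustration only.** From step 1, one such record among 20 can move 4/20 (p = 0.133) to 5/20 (p = 0.043). The documents give no rate of incomplete scores. Suppose a share f of true failures is miscounted as success and nothing is miscounted the other way. The null success rate becomes 0.10 + 0.90f, and the probability of 5 or more successes becomes:

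| Assumed f | 0.10 + 0.90f | P(X ≥ 5) |
|---|---|---|
| 0 | 0.100 | 0.043 |
| 1% | 0.109 | 0.059 |
| 2% | 0.118 | 0.078 |
| 5% | 0.145 | 0.153 |
| 10% | 0.190 | 0.327 |

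These rows show sensitivity to an assumption. They do not estimate what this plan will produce.

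**The case against.** The strongest reply is that such a record may never occur. Four conditions must coincide, and the plan works against blank domains. Protocol 9.1 and 9.2, which Appendix 6 Section 9 applies to the Extension, require omissions to be explained, forms to be checked for completeness and queries to be repeated until resolved. A footnote in Appendix 6 asks for the same investigator to do every mDRS from Visit 7 to Visit 12. SAP 8 allows no remote Extension visits. SAP 7 mentions repeat visits for incomplete ones, with handling settled before database lock. All of this stands, and it makes a low rate likely. None of it changes the classification once a domain stays blank. SAP 3.4 plans no blinded data review for the Extension, and leaving repeat-visit data to a later meeting is not a scoring rule.

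The consequence is also bounded. SAP 6.1, 6.6.1 and 7 make this analysis exploratory and secondary, and the trial is called successful only on the Parent primary endpoint. Individual domains and their changes are summarised, and individual mDRS scores are listed, so the observed Visit 9 values are lost only to the success/failure call.

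A reader might infer that the rule favours success overall. The documents do not show that. A patient who truly improved at Visit 9 but has a blank domain, and who was above the Visit 7 total at Visit 8, is turned into a failure by the same rule. The error runs one way only among the records singled out here. Nor is an all-or-nothing composite wrong in itself; it is a common convention.

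**Conclusion.** The point holds in a limited form. SAP 10.1, read with SAP 6.6 and Protocol Appendix 6 Section 8.6, can score as a success a patient whose recorded Visit 9 data already prove failure. That follows from the text alone, given that 0 is the lowest domain value.

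The frequency is unknown and probably low. The net direction of error over all partly scored visits is not established. The move from 4/20 to 5/20 is the single count at which one record changes significance at n = 20, and it is not a forecast. It would be going too far to say that the Extension test has an inflated error rate, that its power statement is wrong, or that the trial's conclusion is at risk. The documents support none of these. This is a small gap in an exploratory analysis, worth closing because the correct answer is already in the data.

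**What to change.** Add one sentence to SAP 10.1, with a cross-reference in SAP 6.6: if some Visit 9 domains are missing but the observed Visit 9 domains sum to more than the Visit 7 total, the patient is a failure; the Visit 8 substitution applies only where the observed domains do not determine the Visit 9 result. The documents state no maximum for a domain, so on their text observed domains can prove failure but not success.

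I would not add carry-forward of single domains. It assumes no change in the blank domain, which also leans towards success, and it has no defined source at Visit 7.

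The cost is one sentence and minor programming, agreed before the Extension endpoint is analysed. No new data are needed. The success rate can only stay the same or fall slightly.
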